10.0 Efficacy Analysis

10.1 General Considerations

No formal statistical tests will be performed for Japan Sub-Study. Statistical tests will be performed exploratory at the nominal significant level of 0.05. Descriptive statistics will be provided. These include the number of observations, mean, standard deviation, minimum, median, and maximum for continuous variables; and counts and percentages for discrete variables. The analysis will be performed using SAS® (SAS Institute Inc., Cary, NC, USA).

10.2 Primary Efficacy Analysis

This section provides the details of the primary efficacy analysis for the Induction Study.

Primary Efficacy Variable:

The primary efficacy variable for the Induction Study is the proportion of subjects achieving clinical remission (defined as a Full Mayo score ≤ 2 with no subscore > 1) at Week 8.

Analysis Data Set for the Primary Efficacy Analysis:

The primary efficacy analysis will use the I-ITT and J-ITT analysis set for the Induction Study.

Imputation Method used for the Primary Efficacy Analysis:

The primary efficacy analysis will use the NRI method to impute the missing values at Week 8 for the Induction Study. Subjects with missing primary endpoint data at Week 8 will be classified as "Not Achieved."

Statistical Method of the Primary Efficacy Analysis:

The primary analysis of the Induction Study will compare the subjects in the higher adalimumab induction regimen versus the standard adalimumab induction regimen in the ITT analysis set. The difference between the treatment regimens in the proportion of subjects achieving clinical remission at Week 8 will be assessed using Cochran-Mantel-Haenszel (CMH) test adjusted for previous infliximab use and baseline corticosteroid use. A CMH based two-sided 95% confidence interval (CI) for the difference in the proportions between the treatment groups will be calculated. Breslow Day test for homogeneity of odds ratios will be performed as well.

As sensitivity analyses, logistic regression including treatment, the randomization stratification factors, region (US, Japan and other regions) for only the I-ITT analysis set, and additional clinically important factors such as IMM use at Baseline, Baseline CRP, and disease severity at Baseline will also be performed for the primary endpoint.

A cross table of Week 8 responder/remitter status per site reader and central reader within I-ITT and J-ITT will be generated to summarize the discrepancies if there are any.

10.3 Secondary Efficacy Analyses

Ranked secondary efficacy variables (ranked hierarchically in decreasing order) for the Induction Study are:

1. Proportion of subjects achieving endoscopic improvement (endoscopic subscore of 0 or 1) at Week 8.
2. Proportion of subjects with fecal calprotectin below 150 mg/kg at Week 8.
3. Proportion of subjects with IBDQ response (increase of IBDQ ≥ 16 from Baseline) at Week 8.
4. Proportion of subjects achieving clinical response (per Full Mayo score) at Week 8.

5. Proportion of subjects achieving endoscopic remission (endoscopic subscore of 0) at Week 8.
6. Proportion of subjects achieving response in IBDQ Bowel Symptom domain (increase of IBDQ bowel symptom domain score ≥ 6) at Week 8.
7. Proportion of subjects achieving response in IBDQ fatigue item (increase of IBDQ fatigue item score ≥ 1) at Week 8.

As all these endpoints are categorical variables, NRI method of imputation, as described for the primary efficacy analysis, will be used for the missing values.

For Induction Study endpoints, the difference between the higher adalimumab induction treatment group versus the standard adalimumab induction treatment group will be assessed using I-ITT and J-ITT analysis set. The difference in proportions of subjects between treatment groups will be analyzed using the two-sided Cochran-Mantel-Haenszel (CMH) test adjusted for previous infliximab use and baseline corticosteroid use in the ITT analysis set for the secondary endpoints at Week 8. Additionally, the CMH based two-sided 95% confidence interval (CI) for the difference in the proportions between the treatment groups will be calculated.

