- Change from Baseline in fecal calprotectin over time.
- Proportion of subjects with fecal calprotectin below 150 mg/kg over time.
- Time to achievement of remission (per Partial Mayo score).
- Time to achievement of response (per Partial Mayo score).
- Time to loss of response and factors associated with loss of response.
- Change in presence of extraintestinal manifestations.

The difference in proportions of subjects between treatment groups will be analyzed similarly as the ranked secondary endpoints and the CMH based two-sided 95% confidence interval (CI) for the difference in the proportions between the treatment groups will be calculated.

The difference in change from baseline between treatment groups will be analyzed using an ANCOVA model including factors of treatment, stratification variables and Baseline values. Parameter estimates with 95% confidence interval and *P* value will be provided.

NRI for missing data will be used for categorical endpoints. Mixed-Effect Model Repeated Measure (MMRM) model will be applied as the main analysis for the continuous endpoints.

Events of hospitalization and surgery will be identified by blinded adjudication of the serious adverse events (SAEs). Subjects in the integrated safety and Japan safety analysis sets for the Maintenance Study will be included in the all-cause and UC-related hospitalization and surgery rates analyses during the Maintenance Study.

All-cause hospitalization is defined as SAEs resulting in admission to the hospital or prolongation of an existing hospitalization for any reason. UC-related hospitalizations are defined as hospital admissions or prolongation of an existing hospitalization due to AEs or complications that are related to UC and included the following categories: UC-related surgery, hospitalizations for nonsurgical UC-related events, such as UC-related flares, and hospitalizations related to the complications/extra-intestinal manifestations of UC.

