Since subjects do not always adhere to the study visit schedule, the following rules will be applied to assign actual visits to protocol-specified visits including early termination visits. For each study visit mentioned in the protocol, a nominal or target day along with a window around the target day will be selected to represent the corresponding visit. Windows will be selected in a non-overlapping fashion so that a date collected on the CRF does not correspond to multiple visit windows. Moreover, windows will not discard

any post-baseline measurement recorded on the CRF. If a subject had two or more actual visits in one visit window, the visit closest to the target will be used as the study visit for that window. If two visits are equidistant from the target, then the later visit will be used for reporting. If more than one assessment is collected on the same day, then the average of those assessments will be used in analyses.

Table 1. Visit Windows for Analysis of Efficacy Variables, Laboratory Parameters and Vital Signs (Induction Study)

Scheduled Week	Nominal Day	Time Window (Rx Day A Range)
Week 0 ^a	1	≤ 1
Week 1	8	2 – 11
Week 2	15	12 – 22
Week 4	29	23 – 43
Week 8 ^a	57	44 – 71 ^b

Rx Day A = date of visit – date of first study drug injection in the Induction Study + 1

a. hs-CRP and fecal calprotectin collections are scheduled at Screening/Week 0 and Week 8 per protocol.

b. Minimum of Day 71 or the date of the first injection in the Maintenance Study, if applicable.

Table 2. Visit Windows for Analysis of Endoscopy Variables (Induction Study)

Scheduled Week	Nominal Day	Time Window (Rx Day A Range)
Week 0	1	≤ 1
Week 8	57	2 – 71 ^a

Rx Day A = date of visit – date of first study drug injection in the Induction Study + 1

a. Minimum of Day 71 or the date of the first injection in the Maintenance Study, if applicable.

Table 3. Visit Windows for Analysis of IBDQ, SF-36 and WPAI (Induction Study)

Scheduled Week	Nominal Day	Time Window (Rx Day A Range)
Week 0 ^a	1	≤ 1
Week 2	15	2 – 22
Week 4	29	23 – 43
Week 8 ^a	57	44 – 71 ^b

Rx Day A = date of visit – date of first study drug injection in the Induction Period + 1

- a. SF-36 and WPAI collections are scheduled at Week 0 and Week 8 per protocol.
- b. Minimum of Day 71 or the date of the first injection in the Maintenance Study, if applicable.

Definition of Missing Data Imputation

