10.4 Additional Efficacy Analyses

Additional pre-specified endpoints in the Induction Study:

All-cause and UC-related hospitalization and surgery rates during Weeks 0 – 8.

Change from Baseline in histologic score at Week 8.

Proportion of subjects achieving clinical remission per Adapted Mayo Score at Week 8.

Proportion of subjects achieving clinical remission defined as Adapted Mayo score ≤ 2 with no subscore > 1 at Week 8.

Relationship between histologic subscores and endoscopic improvement (endoscopy subscore of 0 or 1) at Week 8.

Relationship between histologic scores and endoscopic subscore of 0 at Week 8.

Proportion of subjects achieving clinical remission per Partial Mayo score over time.
Proportion of subjects achieving clinical response per Partial Mayo score over time.
Proportion of subjects with SFS of 0, RBS of 0 and endoscopic subscore of 0 at Week 8
Proportion of subjects with SFS < 1 over time
Proportion of subjects with RBS of 0 over time
Change from Baseline in hs-CRP over time.
Change from Baseline in IBDQ total and domain score over time.
Proportion of subjects with IBDQ total score ≥ 170 over time.
Change from Baseline in Mayo score, Partial Mayo score, Adapted Mayo score and Mayo subscores over time.
Change from Baseline in laboratory and nutritional parameters (e.g., hemoglobin, hematocrit, albumin, total protein concentration, and weight).
Change from Baseline in subject-reported stool frequency (absolute values).
Change from Baseline in work productivity and impairment questionnaire (WPAI) scores over time.
Change from Baseline in SF-36 score over time.
Change from Baseline in fecal calprotectin over time.
Time to achievement of clinical remission (per Partial Mayo score)
Time to achievement of clinical response (per Partial Mayo score)
Change in presence of extraintestinal manifestations over time.

For categorical variables the difference in proportions of subjects between treatment groups will be analyzed similarly as the ranked secondary endpoints and the CMH based two-sided 95% confidence interval (CI) for the difference in the proportions between the treatment groups will be calculated for I-ITT and J-ITT analysis set.

For the continuous endpoints the difference in change from baseline between treatment groups over time will be analyzed using a Mixed-Effect Model Repeated Measure (MMRM) model including factors of treatment, visit, treatment-by-visit interaction,

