stratification variables and Baseline values. Parameter estimates with 95% confidence interval and *P* value will be provided.

NRI for missing data will be used for categorical endpoints. Mixed-Effect Model Repeated Measure (MMRM) model will be applied for the continuous endpoints, where applicable.

Events of hospitalization and surgery will be identified by blinded adjudication of the serious adverse events (SAEs). Subjects in the safety analysis set for the Induction will be included in the all-cause and UC-related hospitalization and surgery rates analyses during the Induction Study.

All-cause hospitalization is defined as SAEs resulting in admission to the hospital or prolongation of an existing hospitalization for any reason. UC-related hospitalizations are defined as hospital admissions or prolongation of an existing hospitalization due to AEs or complications that are related to UC and included the following categories: UC-related surgery, hospitalizations for nonsurgical UC-related events, such as UC-related flares, and hospitalizations related to the complications/extra-intestinal manifestations of UC.

Unadjusted incidence rates will be used to assess the risk of all-cause and UC-related hospitalization and surgery rates during Weeks 0 – 8. The difference between the two treatment groups will be determined using Chi-square test.

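### The calprotectin <150 mg/kg endpoint is compared without the subject's starting calprotectin: no bias, but some precision is lost and reaching the cut-off is mixed with staying below it

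*SAP*

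**What the plan says.** Induction SAP, section 10.3, lists as ranked endpoint 2: "Proportion of subjects with fecal calprotectin below 150 mg/kg at Week 8". It applies to all randomized subjects in I-ITT and J-ITT. Missing values are handled by non-responder imputation: "NRI method of imputation, as described for the primary efficacy analysis, will be used for the missing values". The CMH test is "adjusted for previous infliximab use and baseline corticosteroid use in the ITT analysis set for the secondary endpoints at Week 8". No rule requires, excludes or stratifies by the starting calprotectin.

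Maintenance SAP, section 10.4, carries the cut-off forward as an additional endpoint: "Proportion of subjects with fecal calprotectin below 150 mg/kg over time". By section 10.1 the default sets are I-ITT-RP and J-ITT-RP, the Week 8 responders. The CMH follows section 10.3 and adjusts for induction regimen and Week 8 responder/remitter status.

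The starting value exists in both periods. The note to Table 1 in section 6.0 of the Induction SAP says: "hs-CRP and fecal calprotectin collections are scheduled at Screening/Week 0 and Week 8 per protocol". Table 3 of the Maintenance SAP has a Maintenance Baseline window for calprotectin.

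The continuous version is treated differently. For "Change from Baseline in fecal calprotectin over time" the induction model (section 10.4) includes "stratification variables and Baseline values".

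**The concern.** A subject at 80 mg/kg at Week 0 and 120 mg/kg at Week 8 has moved the wrong way but counts as a success. In maintenance, responders already below 150 at Week 8 need only stay there, while the others must get there. One rate covers both.

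This sets the endpoint apart from the other ranked induction endpoints. Entry requires a Mayo Score of 6 to 12 with an endoscopy subscore of 2 or 3, so nobody starts in remission or with an endoscopic success. Clinical response and the three IBDQ endpoints are defined by change.

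The starting value is also likely to predict the outcome. Leaving it out of a comparison for which it has already been collected gives up precision at almost no saving. The covariate-adjusted logistic sensitivity analysis in section 10.2 of the Induction SAP covers only the primary endpoint. The induction baseline list (section 7.1) omits calprotectin, although the maintenance list includes it, so the planned induction tables would not show how many subjects began below 150.

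**Working it through.** **Plan figures.** The documents give no expected rate, distribution or correlation for calprotectin, so there is no stated figure to reproduce. The size has to be shown over assumed ranges.

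**Inputs from the documents.** Integrated induction N = 840 + 100 = 940, allocated 3:2, which is 564 higher dose and 376 standard dose. Overall Week 8 response is 50%. Main Study maintenance allocation is 2:2:1, and Japan's is 1:1.

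**Assumptions, induction.** Log calprotectin at Week 0 and Week 8 is bivariate normal with correlation r = 0.2 to 0.6. A share f = 2% to 20% is below 150 at Week 0. Week 8 rates are 20% v 35% (the planned remission rates, borrowed) or 25% v 35%. With x the standardized Week 0 value and z the normal quantile of an arm's overall rate p:

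P(below 150 at Week 8 | x) = Φ((z − r·x) / √(1 − r²))

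**One setting in full: 20% v 35%, f = 5%, r = 0.4.**
- Unadjusted variance: 0.20×0.80/376 + 0.35×0.65/564 = 0.000829, so SE = 0.0288.
- Model rates for subjects starting below 150: 49.2% v 68.2%, a difference of 18.9 points. For the rest: 18.5% v 33.3%, a difference of 14.8 points. Check: 0.05×18.9 + 0.95×14.8 = 15.0.
- Variance stratified by starting status: 0.05×(0.4925×0.5075/376 + 0.6819×0.3181/564) + 0.95×(0.1846×0.8154/376 + 0.3325×0.6675/564) = 0.000807. The term for the differing stratum effects is about 0.0000001.
- Cut: 1 − 0.000807/0.000829 = 2.7%. Using the full starting value instead gives 8.8%.

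**Range over all 24 settings.**

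| Quantity | Lowest | Highest |
|---|---|---|
| Variance cut, stratum <150 v >=150 | 0.3% | 14% |
| Variance cut, full starting value | 2% | 22% |
| SE with full value, 20% v 35% (now 0.0288) | 0.0285 | 0.0256 |
| SE with full value, 25% v 35% (now 0.0300) | 0.0297 | 0.0266 |
| Share of successes already below 150 at Week 0 | 3% | 50% |

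Power at 25% v 35% would rise from 91.5% to between 92.0% and 96.4%. At 20% v 35% it is already 99.9%. Most of the gain comes from the value itself, not from the cut at 150.

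**Maintenance.** Planned responders per arm: 840×0.50×2/5 = 168, plus 100×0.50/2 = 25, giving 193. Assume half are below 150 at Week 8 and remitter status is already in the CMH. Repeated simulations of 3,000 to 4,000 trials show that adding the Week 8 <150 status cuts the variance of the Mantel-Haenszel risk difference by about 2%, 7% to 10%, and 14% to 16% for Week 8-to-Week 52 correlations of 0.3, 0.5 and 0.6.

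**Japan set.** J-ITT has 100 subjects in four strata, with infliximab exposure capped at 25%. At f = 5% there are 100×0.05 = 5 subjects below 150. If 20% had infliximab and half took steroids, each infliximab cell would expect 5×0.20×0.50 = 0.5 of them. One-arm cells drop out of the CMH. At f = 5% the simulated change from the extra stratum was a slight loss (−0.5%).

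**The case against.** The strongest reply is that nothing here is an error. Being below a target at Week 8 is a legitimate endpoint in all randomized subjects, and the induction CMH uses the actual randomization factors. Randomization balances starting values on average, so the comparison is unbiased. All of that stands. The subject who moved from 80 to 120 is also picked up by the continuous change analysis. That is true too, but it does not sharpen or explain the higher-ranked binary result. In maintenance, moreover, Baseline means Week 0, not the Week 8 value.

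The stakes are low. The induction tests are exploratory with no multiplicity adjustment, and the maintenance endpoint is unranked at nominal alpha. An extra CMH stratum would still count subjects already below 150 as successes.

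Two stronger readings are tempting and should not be drawn:
- A reader might infer that subjects already below 150 dilute the risk difference by their share f. That requires all of them to stay below in both arms. In the model above, their treatment difference was larger than that of the other subjects in 21 of 24 settings. The difference among subjects starting at >=150 was 13.6 to 15.0 points against 15 overall, and 9.3 to 10.1 against 10.
- A reader might infer that this undermines the consistency objective. The only quantified consistency criterion (section 4.3 of both SAPs) concerns remission rates, not calprotectin.

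**Conclusion.** The point holds as one of precision and interpretability, and it is minor. Validity is not affected. In induction I-ITT, separating by starting status would cut the variance of the risk difference by 0.3% to 14%, and using the full value would cut it by 2% to 22%. In maintenance the cut is about 2% to 15%. These figures rest on an assumed bivariate-normal model, an assumed share below 150 and assumed correlations. With few subjects below 150 at entry and a weak correlation, the gain is close to nil. A subject who starts below 150 counts as a success only if the later value is observed and still below 150, because missing values are scored as not achieved. The interpretive point does not depend on the model: as planned, the rate cannot be split into subjects who reached the cut-off and subjects who remained below it.

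**What to change.** Keep the planned CMH analyses. For this endpoint, add:

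- **Integrated sets:** an analysis adjusted for the starting value, for example logistic regression with a standardized risk difference. Use log Baseline calprotectin in induction (I-ITT) and log Maintenance Baseline calprotectin in maintenance (I-ITT-RP). Keep non-responder imputation and the existing adjustment factors.
- **Integrated and Japan sets:** the rate shown descriptively by starting status (<150 versus >=150 mg/kg), with the number in each group. In maintenance this separates subjects who stayed below from those who came down.
- **J-ITT:** do not add the extra CMH stratum.

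The cost is SAP wording, one supportive model, one table layout per period, and a rule for subjects with no starting sample (for example a missing indicator). No new data are needed.

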10.4 Additional Efficacy Analyses

Additional pre-specified endpoints in the Induction Study:

All-cause and UC-related hospitalization and surgery rates during Weeks 0 – 8.

Change from Baseline in histologic score at Week 8.

Proportion of subjects achieving clinical remission per Adapted Mayo Score at Week 8.

Proportion of subjects achieving clinical remission defined as Adapted Mayo score ≤ 2 with no subscore > 1 at Week 8.

Relationship between histologic subscores and endoscopic improvement (endoscopy subscore of 0 or 1) at Week 8.

Relationship between histologic scores and endoscopic subscore of 0 at Week 8.

Proportion of subjects achieving clinical remission per Partial Mayo score over time.
Proportion of subjects achieving clinical response per Partial Mayo score over time.
Proportion of subjects with SFS of 0, RBS of 0 and endoscopic subscore of 0 at Week 8
Proportion of subjects with SFS < 1 over time
Proportion of subjects with RBS of 0 over time
Change from Baseline in hs-CRP over time.
Change from Baseline in IBDQ total and domain score over time.
Proportion of subjects with IBDQ total score ≥ 170 over time.
Change from Baseline in Mayo score, Partial Mayo score, Adapted Mayo score and Mayo subscores over time.
Change from Baseline in laboratory and nutritional parameters (e.g., hemoglobin, hematocrit, albumin, total protein concentration, and weight).
Change from Baseline in subject-reported stool frequency (absolute values).
Change from Baseline in work productivity and impairment questionnaire (WPAI) scores over time.
Change from Baseline in SF-36 score over time.
Change from Baseline in fecal calprotectin over time.
Time to achievement of clinical remission (per Partial Mayo score)
Time to achievement of clinical response (per Partial Mayo score)
Change in presence of extraintestinal manifestations over time.

For categorical variables the difference in proportions of subjects between treatment groups will be analyzed similarly as the ranked secondary endpoints and the CMH based two-sided 95% confidence interval (CI) for the difference in the proportions between the treatment groups will be calculated for I-ITT and J-ITT analysis set.

For the continuous endpoints the difference in change from baseline between treatment groups over time will be analyzed using a Mixed-Effect Model Repeated Measure (MMRM) model including factors of treatment, visit, treatment-by-visit interaction,

stratification variables and Baseline values. Parameter estimates with 95% confidence interval and *P* value will be provided.

NRI for missing data will be used for categorical endpoints. Mixed-Effect Model Repeated Measure (MMRM) model will be applied for the continuous endpoints, where applicable.

Events of hospitalization and surgery will be identified by blinded adjudication of the serious adverse events (SAEs). Subjects in the safety analysis set for the Induction will be included in the all-cause and UC-related hospitalization and surgery rates analyses during the Induction Study.

All-cause hospitalization is defined as SAEs resulting in admission to the hospital or prolongation of an existing hospitalization for any reason. UC-related hospitalizations are defined as hospital admissions or prolongation of an existing hospitalization due to AEs or complications that are related to UC and included the following categories: UC-related surgery, hospitalizations for nonsurgical UC-related events, such as UC-related flares, and hospitalizations related to the complications/extra-intestinal manifestations of UC.

Unadjusted incidence rates will be used to assess the risk of all-cause and UC-related hospitalization and surgery rates during Weeks 0 – 8. The difference between the two treatment groups will be determined using Chi-square test.

